Project Title: Reducing the Burden of Chronic Psychotic Disorders in Tanzania (CAPACITY)

Principal Investigators: [name] MD and [name] MD

Co-Investigators: [name] PhD, [name] MD, [name] PhD, and [name] PhD

Protocol Version Date: January 7, 2019

Overview: Antipsychotic medication is a critical component of treatment for individuals with chronic psychotic disorders (CPDs) in conjunction with psychosocial approaches that support patients and families. Unfortunately, poor medication adherence is common, impedes recovery and increases burden. In Sub-Saharan Africa (SSA), poor adherence is seen in approximately half of individuals with CPD and is a major driver of relapse ⁽⁶⁻¹⁰⁾. Care approaches that promote adherence, take advantage of existing resources and which can be readily scaled and implemented in SSA settings, have the potential to greatly advance care and reduce the burden of CPD.

The burden of CPD in Africa: In SSA, brain disorders are the most disabling conditions among people ages 10–44 ⁽¹¹⁻¹²⁾. CPD causes symptoms such as hallucinations, delusions, disorganized communication, poor planning, and reduced motivation. Quality of life is impaired and personal and occupational goal attainment is sub-optimal. Care for CPD includes both psychosocial and pharmacologic interventions (i.e. antipsychotic drugs) along with ongoing monitoring of health status ⁽¹³⁾. This may be challenging in resource-limited settings where staff are sparse and/or undertrained. Importantly, forecasts of mental health human resource demands predict continued deficits compounded by increasing disease burden ⁽¹⁴⁾.

CPD relapse results in hospitalization, treatment resistance, and cognitive impairment due to progressive structural brain damage ⁽¹⁵⁾. The limited number of CPD relapse studies done in Africa suggest that co-morbid depression, poor medication adherence, and side-effects are the factors most likely to increase relapse ⁽¹⁶⁾. A Tanzanian study found that people with CPD and their caregiver's perceived non adherence to antipsychotic medication as a leading risk factor of relapse ⁽¹⁰⁾.

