
Aim 2: After completion of the Aim 1 assessments, the study team will adapt a successful CPD adherence enhancement approach (Phase 2) based upon findings from Phase 1. Like the original CAE-L program, the intervention will be described in a detailed manual /curriculum that will facilitate future broad-scale dissemination.

Aim 3: In Phase 3/Aim 3, the study team will select appropriate measures, train staff and build capacity in measure implementation, and finalize the intervention for delivery by healthcare workers. Finally, in a training/proof-of-concept exercise, the healthcare workers will implement the adapted CAE-L in a high-risk sample of Tanzanians with CPD (individuals with schizophrenia or schizoaffective disorder who have had recent medication adherence problems). Taken together, the proposed project has substantial public health importance. It will provide the prerequisite materials, training and infrastructure needed for a prospective trial in reducing CPD burden and improving brain health in Tanzania and other countries in Sub-Saharan Africa.

Study Design:

Phase 1

In Phase 1/Aim 1 the investigators will implement a mixed-methods (quantitative + qualitative) adherence assessment battery that will identify salient barriers to treatment adherence in people with CPD. Data collection and procedures will follow those previously successfully used by this team. Qualitative assessment will be conducted using a combination of individual and group-format methodologies. A “deliverable” of Phase 1 will be a summary report that describes barriers and facilitators to treatment for CPD from the perspective of patients, families and care providers.

Quantitative assessment: Drawn from iterative pilot work (32,36 40-41), CAE is flexibly delivered as a series of up to 4 treatment modules whose use is determined based upon an individual's reasons for non-adherence (adherence barriers) identified at baseline. The modules are Psychoeducation focused on medication and consequences of missing medication, Modified Motivational Enhancement Therapy (MET) to address non-adherence related to substance use, Communication with Providers to facilitate appropriate treatment expectations and optimize management of feared or experienced side effects, and Medication Routines intended to incorporate medication-taking into lifestyle. Prior to delivering CAE,

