Focus group format: Up to 16 adult (\geq age 18) family members of individuals with CPD will be invited to participate in 2 focus groups conducted by [name] and trainees at the Tanzania site. Family members will all have regular contact with patients (contact a minimum of 3 days/week). Family member focus groups will comprise 6-10 individuals each, and will last up to approximately 90 minutes. Focus groups will be audio-recorded and transcribed verbatim and supplemented with the addition of copious field-notes. Up to 16 health workers will be invited to participate in 2 additional focus groups, using similar format as the family focus groups. Health workers (nurses, doctors, social workers, pharmacists) will be recruited from clinic and hospital-based settings and have experience interacting with patients with CPD. *Individual interview format:* Up to 15 patients with CPD will be interviewed regarding barriers and facilitators to medication adherence. Data recording will be the same as with focus groups.

Phase 2

In Phase 2/Aim 2, informed by the mixed-methods data from Phase 1, the study team will adapt the CAE-L intervention to be culturally and linguistically appropriate for the Tanzanian setting. The “deliverable” of Phase 2 will include a manualized intervention that combines a psychosocial intervention to promote adherence + use of LAI.

Phase 3

In Phase 3/Aim 3, the study team will select appropriate measures, train staff in measure implementation, and finalize CAE-L for delivery. Social worker interventionists will be trained to deliver CAE-L. Finally, the study will roll-out and evaluate CAE-L in 20 individuals with CPD in a 6-month (25-week) prospective training/proof-of-concept exercise. CAE-L will be further refined based upon input from interventionists and study participants. The “deliverable” of Phase 3 will include building capacity of a clinical trials infrastructure that includes identification of relevant tools/ measures and appropriately trained staff who are capable and available to conduct research to improve health outcomes for people with CPD in Tanzania.

Phase 3 Study Population:

The study will enroll 20 adult patients with the following criteria:

Inclusion Criteria:

1. Individuals age 18 and older with schizophrenia or schizoaffective disorder.

2. Known to have medication treatment adherence problems as identified by the TRQ (20% or more missed medications in past week or past month)

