3. Ability to be rated on psychiatric rating scales.
4. Willingness to take long-acting injectable medication
5. Able to provide written, informed consent to study participation.

Exclusion Criteria:

1. History of allergy or intolerance to haloperidol or haloperidol decanoate.
2. Individuals on long-acting injectable antipsychotic medication immediately prior to study enrollment.
3. Medical condition or illness, which in the opinion of the research psychiatrist, would interfere with the patient's ability to participate in the trial.
4. Physical dependence on substances (alcohol or illicit drugs) likely to lead to withdrawal reaction during the course of the study in the clinical opinion of the treated research psychiatrist.
5. Immediate risk of harm to self or others.
6. Female who is currently pregnant or breastfeeding.

A Screening Form for each patient will be completed regardless of whether the patient is ultimately enrolled. The form will detail reasons for exclusion, allowing an estimate of sample generalizability. All study procedures will be conducted at Muhimbili Hospital and its associated ambulatory clinics.

LAI: Patients on oral haloperidol will be switched to haloperidol decanoate as per manufacturer's package insert. Individuals not on antipsychotic medication at the time of screening assessment or who are on a different antipsychotic medication, will receive an oral tolerance test (OTT) consisting of up to 14 days of oral haloperidol 2-5 mg twice daily. If the OTT suggests good tolerability, the participant will then receive LAI (haloperidol decanoate) intramuscularly after completion of baseline assessments. Dosing of LAI will be as clinically indicated using conservative dosing to minimize drug-related adverse effects. In the CWRU studies, mean end-point dose of haloperidol decanoate was 68.0 mg, SD 21.1, Range 50-100 mg/monthly injection. It is anticipated that patients will continue on the same dose for 6 months, although dose changes will be permitted based upon clinical status. Each study participant will receive up to 8 injections during the study.

Concomitant treatments: Stable dose psychotropic drugs (> 30 days of previous use) other than antipsychotics will be continued. New psychotropic medications will be strongly discouraged. Medications for side effects may be given at the discretion of the treating psychiatrist and their use will be recorded.

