Alcohol and Substance Use: The 10-item version of the Alcohol Use Disorders Identification Test (AUDIT) will be used to assess alcohol use (Saunders et al, 1993). The Alcohol, Smoking and Substance Involvement Screening Test (ASSIST) will be used to measure drug use (World Health Organisation ASSIST Working Group, 2002).

Health Resource Use: Resources that are typically utilized by the most severely ill individuals with schizophrenia include emergency care and hospitalization. Resource use in the 6-month period prior to study enrollment and in the 6-month study period will be evaluated.

Safety/Laboratory Evaluations: Safety evaluations will include basic laboratory evaluations (serum comprehensive metabolic panel, lipid profile, CBC with differential, and HIV as well as urine pregnancy testing for women) and EKG. Patient vital signs and weight will be collected at each study visit. Standardized measures of extrapyramidal symptoms will be assessed with the Extrapyramidal Symptoms Scale-Abbreviated version (ESRS-A). Finally, reported side effects will also be evaluated at each study visit using a standardized form developed in the CAE-L studies conducted at CWRU (Appendix 4)

Other Outcomes of Interest:

Attitude toward Medication Questionnaire (AMQ): A modification of the Lithium Attitudes Questionnaire, the AMQ evaluates an individual's attitudes towards psychiatric medication. The AMQ comprises 19 items grouped into 7 subscales: general opposition to prophylaxis (4 items), denial of therapeutic effectiveness (2 items), fear of side effects (2 items), difficulty with medication routines (4 items), denial of illness severity (3 items), negative attitudes toward drugs in general (3 items), and lack of information about psychiatric medication (1 item). Higher scores on each subscale represent more negative attitudes toward mood stabilizers.

Rating of Medication Influences (ROMI), is a measure of attitudes towards medication treatment that was originally developed for populations with schizophrenia. For this project we will be using Part II of the ROMI, which contains 10 items that directly inquire about influences leading to non-adherence. The ROMI has been found to be reliable, clinically sound and valid compared with other independent measures of attitudes toward medications and compliance.

Vulnerable populations:

Pregnant Women

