Component 2: [name] & [name] will co-lead regular research staff meetings to closely monitor study start-up and progress, including oversight of staff training and research capacity building. These meetings (held via SKYPE conference will be held approximately every other week for the first 3 months of the project and then at least once a month by web teleconference thereafter. Meeting minutes will be sent to all research staff participants. Regularly scheduled conference calls will be supplemented by more frequent local meetings and ad-hoc meetings that may be called in the event that problems or concerns arise. In addition, there will be 1-2 in-person visits to the sites annually. Any adverse or unexpected events will be reported in accordance with local IRB requirements.

Statistical Analysis:

Phase 1: First, the qualitative team will first independently review each transcript and highlight significant statements, sentences, or quotes. Based on review of the independently derived statements, the team will develop consensus-based “clusters of meaning” (58) or relevant “themes and categories” (58). Researchers will further read/code each document independently and iteratively until no new insights emerge.

These entries will be elaborated as coding progresses. The qualitative researchers will then construct a consensus-based coding dictionary that includes mutually exclusive definitions for each code. This coding structure will be reviewed after a preliminary analysis of a sub sample of transcripts, and the dictionary will be refined through comparison, categorization, and discussion (59-60). Then, using data and codes, the qualitative team will create code-based files across all

respondents. The team will further elaborate, refine, and differentiate the codes and identify similarities and differences through comparison of respondents.

Phase 3: Quantitative analysis will be limited as the focus is on feasibility, patient acceptability and research capacity-building. However, we will assess descriptive statistics and change from baseline in the primary and secondary measures using standard pre-post techniques.

References:

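### If Phase 3 participants are recruited during or soon after an admission or emergency visit, the before/after comparison of resource use counts that event only in the before period and can show a fall with no effect of CAE-L

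*Combined protocol and SAP*

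**What the plan says.** Under Secondary Outcome, the Health Resource Use paragraph names what is counted: "Resources that are typically utilized by the most severely ill individuals with schizophrenia include emergency care and hospitalization". It then sets the comparison: "Resource use in the 6-month period prior to study enrollment and in the 6-month study period will be evaluated". Table 1 schedules the measure at baseline, Week 13 and Week 25.

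The Phase 3 part of Statistical Analysis provides descriptive statistics and "change from baseline in the primary and secondary measures using standard pre-post techniques". There is no control group. On sample size, Phase 3 Study Population says: "The study will enroll 20 adult patients with the following criteria".

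Entry rests on missed medication. The second inclusion criterion reads "Known to have medication treatment adherence problems as identified by the TRQ (20% or more missed medications in past week or past month", and Aim 3 describes the sample as "individuals with schizophrenia or schizoaffective disorder who have had recent medication adherence problems". On setting, the same section says: "All study procedures will be conducted at Muhimbili Hospital and its associated ambulatory clinics". The section on the burden of CPD links relapse to admission: "CPD relapse results in hospitalization, treatment resistance, and cognitive impairment".

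No section says how an admission or emergency visit that leads to enrollment, or is still ongoing at enrollment, is to be counted. The unit (events or days) is not defined either.

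**The concern.** The look-back closes on the day of enrollment. A participant found during or just after an admission therefore brings at least that one event into the before count. The study period has no matching event built in. The two windows are of equal nominal length, but that does not help, because the problem is which event is counted and not how long the counting lasts.

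Such recruitment is plausible. Phase 3 selects on recent non-adherence, the protocol's Overview names poor adherence as a main cause of relapse, and the work is done at a hospital and its clinics.

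With one arm, a fall in admissions cannot be separated from the timing of recruitment. The figure could still be quoted as reduced burden, which is the subject of the project title. The section on major psychiatric illness also describes the study as one of effectiveness.

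**Working it through.** The plan gives no admission rate, power calculation or significance level, so there is no figure of its own to reproduce. The check asks what the planned comparison would show if CAE-L had no effect.

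**Inputs**
- N = 20, one group (Phase 3 Study Population).
- Two windows of 6 months each (Health Resource Use).
- r, the background number of events per person per 6 months: not in the documents. Assumed 0.2 and 0.5.
- k, the number of participants who enter through an index event: not in the documents. Assumed 0, 5 and 10.

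**Step 1: expected counts with no effect**

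Before = 20r + k. After = 20r. Apparent fall = k/(20r + k).

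| r | k | Before | After | Apparent fall |
|---|---|---|---|---|
| 0.2 | 0 | 4 | 4 | 0% |
| 0.2 | 5 | 9 | 4 | 5/9 = 56% |
| 0.2 | 10 | 14 | 4 | 10/14 = 71% |
| 0.5 | 0 | 10 | 10 | 0% |
| 0.5 | 5 | 15 | 10 | 5/15 = 33% |
| 0.5 | 10 | 20 | 10 | 10/20 = 50% |

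**Step 2: how often a single trial would show a fall**

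This was simulated with 20,000 trials of 20 participants per setting. Background events were Poisson with mean 0.25 in each window, and a share f of participants had one added index event in the before window. The plan names no test or level for this measure, so the two-sided 0.05 sign test and paired t-test are illustrative.

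| f | Total falls | Significant fall, sign test | Significant fall, paired t |
|---|---|---|---|
| 0 | 44% | 0.8% | 2.3% |
| 0.25 | 89% | 15.5% | 25.1% |
| 0.5 | 99% | 57.2% | 69.4% |

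**Step 3: what happens if recent events are left out**

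The analyst cannot tell an event that led to recruitment from one that happened by chance shortly before it. Take 6 months as 182 days and a constant rate. Leaving out every event of the last 30 days then also removes 20r × 30/182 chance events on average: 0.66 at r = 0.2 and 1.65 at r = 0.5. If k = 0, the before count covers only 152 days, and after/before = 182/152 = 1.20, an apparent rise of 20%. So the count with recent events errs toward a fall, and the count without them errs toward a rise. Neither should stand alone.

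**Step 4: what the arithmetic does not cover**

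Even with k = 0, people chosen at a time of poor adherence probably had more events than usual just before entry. Some return toward their usual level is expected. The documents give nothing from which to compute its size.

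**The case against.** A reader might infer that an admission brings each patient into Phase 3, so that the comparison must show a fall. The documents do not support this. Phase 3 entry depends on missed medication, and no criterion asks for an admission. The description of participants as recently hospitalized with relapse belongs to Aim 1 and the Phase 1 sample. The sentence about Muhimbili Hospital says where procedures take place, not how patients are found, and it names ambulatory clinics as well. Participants must be ratable and able to give written consent, and immediate risk of harm is an exclusion. These conditions may limit enrollment during an acute admission, though not soon after discharge.

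The sizes also rest on assumed values of r and k. If days were counted instead of events, a patient still in hospital at enrollment would carry the rest of the stay into the study period, which would offset part of the bias.

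Finally, the plan says only that resource use in the two periods will be evaluated. It attaches no hypothesis to it. Both sentences that list the secondary outcomes (Study Measures and Phase 3 Study Measures) omit it, and Statistical Analysis limits the quantitative work because Phase 3 is about feasibility, acceptability and capacity.

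All of this stands. It makes the bias conditional and lowers its importance. It does not supply the missing counting rule, and it does not make an uncontrolled fall interpretable.

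**Conclusion.** The point holds in conditional form. Followed exactly, the plan counts an index admission or emergency visit in the before period only. For every participant recruited that way, the comparison tilts toward a fall that owes nothing to CAE-L. If 5 of 20 enter this way, the apparent fall with no effect is 33% to 56% for r from 0.5 down to 0.2. If none do, the index-event bias is zero. The documents do not say which case applies, so neither a certain bias nor its absence can be claimed.

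The result assumes the same background rate in both windows and a count of events, not days. Regression to the mean from selecting on recent non-adherence would come on top and cannot be quantified here. The priority is low: this is a descriptive measure outside the listed secondary outcomes, in a proof-of-concept exercise.

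**What to change.** In the Health Resource Use paragraph:

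1. Keep both 6-month windows as stated.
2. Record the dates of any admission or emergency visit that is ongoing at enrollment or fell in the preceding 30 days.
3. Report how many participants had such an event.
4. Present the before/after counts both with and without these events, and say that the two are to be read together because leaving them out also removes some chance events.
5. State that the comparison is descriptive and that the change is not attributed to CAE-L.

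Moving the windows, so that the look-back ends before the index event and the study count starts at discharge, may look neater but should be avoided. Take an admission 30 days and a discharge 20 days before enrollment, with the outer dates fixed. The windows become 182 − 30 = 152 and 182 + 20 = 202 days, and 202/152 = 1.33 is a 33% rise at a constant rate. It would also put time before consent and before treatment into the study period.

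The cost is one extra date field, a few sentences and a less favorable before/after figure. The rule should be set before data collection, because index dates may be hard to recover later. It does not remove regression to the mean, which is why the last statement is needed.

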* Screening and baseline assessments may be completed in a single visit if it is more convenient for the participant

** May require additional baseline booster injection depending on dosage
